10.2. Criteria for Potentially Clinically Significant Values (PCSV)

Regeneron Pharmaceuticals, Inc.

Parameter	PCSV	Comments
Total Bilirubin*	>1.5 and \leq 2 ULN and baseline \leq 1.5 ULN* >2 ULN and baseline \leq 2.0 ULN	Must be expressed in ULN, not in µmol/L or mg/L. Categories are cumulative.
		Concept paper on DILI – FDA draft Guidance Oct 2007.
		* At least one level is required, multiple levels are optional for phase 2/3 studies. If it is desirable to get the distribution of significant level, additional shift table on ≤ 1.5 , >1.5 to ≤ 2.0 and > 2.0 category for baseline vs. post baseline may be provided
Conjugated Bilirubin	>35% Total Bilirubin and TBILI>1.5 ULN, and baseline Total Bilirubin \leq 35% or TBILI \leq 1.5 ULN	Conjugated bilirubin determined on a case-by-case basis.
ALT and Total Bilirubin	ALT>3 ULN and TBILI>2 ULN, and baseline ALT \leq 3 ULN or TBILI \leq 2ULN	Concept paper on DILI – FDA draft Guidance Oct 2007.
CPK*	>3 and ≤ 10 ULN and baseline ≤ 3 ULN*	FDA Feb 2005.
	>10 ULN and baseline ≤ 10 ULN	Am J Cardiol April 2006.
		Categories are cumulative.
		* At least one level is required, multiple levels are optional for phase 2/3 studies. If it is desirable to get the distribution of significant level, additional shift table on ≤ 3 , ≥ 3 to ≤ 10 , and ≥ 10 category for baseline vs. post baseline may be provided
Creatinine	\geq 150 µmol/L (Adults) or \geq ULN (if ULN \geq 150 µmol/L) and	Benichou C., 1994.
	baseline < 150 μmol/L or <uln (if="" l)<="" td="" uln≥150="" μmol="">3 independent criteria	</uln>	3 independent criteria
	≥30% change from baseline	
	≥100% change from baseline	

Parameter	PCSV	Comments
Creatinine	<15 ml/min and baseline \geq 15 ml/min (end stage renal	Use is optional.
Clearance	impairment)	FDA draft guidance 2010
(Cockcroft's formula)	\geq 15 -<30 ml/min and baseline \geq 30 ml/min (severe renal impairment)	Four independent criteria, will provide additional shift table if needed
	≥30 - < 60 ml/min and baseline ≥60 ml/min (moderate renal impairment)	
	≥60 - < 90 ml/min and baseline ≥90 ml/min (mild renal impairment)	
Uric Acid		Harrison- Principles of Internal Medicine 17th Ed., 2008.
Hyperuricemia:	>408 μmol/L or >ULN (if ULN≥408 μmol/L) and baseline ≤408 μmol/L or ≤ULN (if ULN≥408 μmol/L)	Two independent criteria
Hypouricemia:	<120 μ mol/L or <lln (if="" <math="" lln≤120="">\mumol/L) and baseline ≥ 120 μmol/L or ≥LLN (if LLN≤120 μmol/L)</lln>	
Blood Urea Nitrogen	≥17 mmol/L or ≥ULN (if ULN≥17 mmol/L) and baseline <17 mmol/L or <uln (if="" l)<="" mmol="" td="" uln≥17="">Two independent criteria	</uln>	Two independent criteria
Chloride		Two independent criteria
Hypochloremia:	<80 mmol/L or <lln (if="" and="" baseline
≥ 80 mmol/L or ≥LLN (if LLN≤80 mmol/L)</lln>	
	>115 mmol/L or >ULN (if ULN≥115 mmol/L) and baseline ≤ 115 mmol/L or ≤ULN (if ULN≥115 mmol/L)	
Hyperchloremia:		
Sodium		Two independent criteria
Hyponatremia:	≤129 mmol/L or ≤LLN (if LLN≤129 mmol/L) and baseline > 129 mmol/L or >LLN (if LLN≤129 mmol/L)	
	≥160 mmol/L or ≥ULN (if ULN≥160 mmol/L) and baseline <160 mmol/L or <uln (if="" l)<="" mmol="" td="" uln≥160="">	</uln>	
Hypernatremia:		

Regeneron Pharmaceuticals, Inc.

CONFIDENTIAL

Parameter	PCSV	Comments
Potassium		FDA Feb 2005.
Hypokalemia	<3 mmol/L or <lln (if="" lln<math="">\leq3 mmol/L) and baseline \geq 3 mmol/L or \geqLLN (if LLN\leq3 mmol/L)</lln>	Two independent criteria
	≥5.5 mmol/L or ≥ULN (if ULN≥5.5 mmol/L) and baseline <5.5 mmol/L or <uln (if="" l)<="" mmol="" td="" uln≥5.5="">	</uln>	
Hyperkalemia		
Total Cholesterol	≥7.74 mmol/L or ≥ULN (if ULN≥7.74 mmol/L) and baseline < 7.74 mmol/L or <uln (if="" l)<="" mmol="" td="" uln≥7.74="">Threshold for therapeutic intervention.	</uln>	Threshold for therapeutic intervention.
Triglycerides	≥4.6 mmol/L or ≥ULN (if ULN≥4.6 mmol/L) and baseline < 4.6 mmol/L or <uln (if="" l)<="" mmol="" td="" uln≥4.6="">Threshold for therapeutic intervention.	</uln>	Threshold for therapeutic intervention.
Lipasemia	\geq 3 ULN and baseline < 3 ULN	
Amylasemia	\geq 3 ULN and baseline < 3 ULN	
Glucose		
	\leq 3.9 mmol/L and \leq LLN and baseline $>$ 3.9 mmol/L or \geq LLN	ADA Jan 2008.
Hypoglycaemia	≥11.1 mmol/L (unfasted); ≥7 mmol/L (fasted) and baseline < 11.1 mmol/L (unfasted); <7 mmol/L (fasted)	
Hyperglycaemia		
HbA1c	$>8\%$ and baseline $\leq 8\%$	
Albumin	\leq 25 g/L or \leq LLN (if LLN \leq 25 g/L) and baseline >25 g/L or >LLN (if LLN \leq 25 g/L)	
CRP	>2 ULN or >10 mg/L (if ULN not provided) and baseline ≤2 ULN or ≤10 mg/L (if ULN not provided)	FDA Sept 2005.

Parameter	PCSV	Comments
Hematology		
WBC	<3.0 Giga/L or <lln (if="" and="" baseline="" giga="" l)="" lln≤3.0="" ≥3.0
Giga/L or ≥LLN (if LLN≤3.0 Giga/L) (Non-Black); <2.0 Giga/L or <lln (if="" and="" baseline="" giga="" l)="" lln≤2.0="" ≥2.0
Giga/L or ≥LLN (if LLN≤2.0 Giga/L) (Black)*</lln></lln>	Increase in WBC: not relevant. *The default criteria. Summary by race (black and Non- black) are optional. To be interpreted only if no differential count available.
	≥16.0 Giga/L or ≥ULN (if ULN≥16.0 Giga/L) and baseline < 16 Giga/L or <uln (if="" giga="" l)<="" td="" uln≥16.0="">	</uln>	
Lymphocytes	>4.0 Giga/L or >ULN (if ULN \geq 4.0 Giga/L) and baseline \leq 4.0 Giga/L or \leq ULN (if ULN \geq 4.0 Giga/L)	
Neutrophils	<1.5 Giga/L or <lln (if="" for="" giga="" l)="" lln≤1.5="" non-black="" or
<1.0 Giga/L or <lln (if="" and="" baseline
≥1.5 Giga/L or ≥LLN (if LLN≤1.5 Giga/L) for Non-Black or ≥1.0 Giga/L or ≥LLN (if LLN≤1.0 Giga/L) for Black*</lln></lln>	International Consensus meeting on drug-induced blood cytopenias, 1991. *The default criteria. By race (black and Non-black) are optional.
	<1.5 Giga/L or <lln (if="" and="" baseline="" giga="" l)="" lln≤1.5="" ≥1.5
Giga/L or ≥LLN (if LLN≤1.5 Giga/L) (Non-Black); <1.0 Giga/L or <lln (if="" and="" baseline="" giga="" l)="" lln≤1.0="" ≥1.0
Giga/L or ≥LLN (if LLN≤1.0 Giga/L) (Black)</lln></lln>	
	<0.5 Giga/L regardless of baseline value or racce	
Monocytes	>0.7 Giga/L or >ULN (if ULN≥0.7 Giga/L) and baseline ≤ 0.7 Giga/L or ≤ULN (if ULN≥0.7 Giga/L)	
Basophils	>0.1 Giga/L or >ULN (if ULN \geq 0.1 Giga/L) and baseline \leq 0.1 Giga/L or \leq ULN (if ULN \geq 0.1 Giga/L)	
Eosinophils	>0.5 Giga/L or >ULN (if ULN≥0.5 Giga/L) and baseline ≤0.5 Giga/L or ≤ULN (if ULN≥0.5 Giga/L)	Harrison- Principles of Internal Medicine 17 th Ed., 2008.

Regeneron Pharmaceuticals, Inc.

CONFIDENTIAL

Parameter	PCSV	Comments
Hemoglobin	\leq 115 g/L or \leq LLN (if LLN \leq 115 g/L) for male or \leq 95 g/L or \leq LLN (if LLN \leq 95 g/L) for female and baseline > 115 g/L or	Three criteria are independent.
	>LLN (if LLN≤115 g/L) for male or >95 g/L or >LLN (if LLN≤95 g/L) for Female*	*The default criteria. By gender (male and female) are optional.
	\leq 115 g/L or \leq LLN (if LLN \leq 115 g/L) and baseline > 115 g/L or >LLN (if LLN \leq 115 g/L) for male;	Criteria based upon decrease from baseline are more relevant than based on absolute value. Other categories for
	≤95 g/L or ≤LLN (if LLN≤95 g/L) and baseline > 95 g/L or >LLN (if LLN≤95 g/L) for Female.	decrease from baseline can be used (\geq 30 g/L, \geq 40 g/L, \geq 50 g/L).
	≥185 g/L or ≥ULN (if ULN≥185 g/L) for male or ≥165 g/L or ≥ULN (if ULN≥165 g/L) for female and baseline <185 g/L or	
	<uln (if="" <165="" <uln="" female*<="" for="" g="" l="" l)="" male="" or="" td="" uln≥165="" uln≥185="">	</uln>	
	≥185 g/L or ≥ULN (if ULN≥185 g/L) and baseline <185 g/L or <uln (if="" for="" g="" l)="" male;<="" td="" uln≥185="">	</uln>	
	≥165 g/L or ≥ULN (if ULN≥165 g/L) and baseline < 165 g/L or <uln (if="" female<="" for="" g="" l)="" td="" uln≥165="">	</uln>	
	Decrease from Baseline ≥20 g/L	

Regeneron Pharmaceuticals, Inc.

Parameter	PCSV	Comments
Hematocrit	\leq 0.37 v/v or \leq LLN (if LLN \leq 0.37 v/v) for Male or \leq 0.32 v/v or \leq LLN (if LLN \leq 0.32 v/v) for Female and baseline > 0.37 v/v or >LLN (if LLN \leq 0.37 v/v) for Male or > 0.32 v/v or >LLN (if LLN \leq 0.32 v/v) for Female*	Two Criteria are independent *The default criteria. By gender (male and female) are optional.
	\leq 0.37 v/v or \leq LLN (if LLN \leq 0.37 v/v) and baseline > 0.37 v/v or >LLN (if LLN \leq 0.37 v/v) for Male ; \leq 0.32 v/v or \leq LLN (if LLN \leq 0.32 v/v) and baseline > 0.32 v/v or >LLN (if LLN \leq 0.32v/v) for Female	
	\geq 0.55 v/v or \geq ULN (if ULN \geq 0.55 v/v) for Male or \geq 0.5 v/v or \geq ULN (if ULN \geq 0.5 v/v) for Female and baseline < 0.55 v/v or <uln (if="" uln<math="">\geq0.55 v/v) for Male < 0.5 v/v or <uln (if
ULN\geq0.5 v/v) for Female*</uln></uln>	
	$\geq 0.55 \text{ v/v or} \geq \text{ULN (if ULN} \geq 0.55 \text{ v/v) and baseline} < 0.55 \text{ v/v or} \\ < \text{ULN (if ULN} \geq 0.55 \text{ v/v) for Male;} \geq 0.5 \text{ v/v or} \geq \text{ULN (if} \\ \text{ULN} \geq 0.5 \text{ v/v) and baseline} < 0.5 \text{ v/v or} < \text{ULN (if ULN} \geq 0.5 \text{ v/v)} \\ \text{for Female} \end{cases}$	
RBC	≥6 Tera/L or ≥ULN (if ULN≥6 Tera/L) and baseline < 6 Tera/L or <uln (if="" l)<="" td="" tera="" uln≥6="">Unless specifically required for particular drug development, the analysis is redundant with that of Hb.	</uln>	Unless specifically required for particular drug development, the analysis is redundant with that of Hb.
Platelets	<100 Giga/L or <lln (if="" and="" baseline="" giga="" l)="" lln≤100="" ≥100
Giga/L or ≥LLN (if LLN≤100 Giga/L)</lln>	International Consensus meeting on drug-induced blood cytopenias, 1991.
	≥700 Giga/L or ≥ULN (if ULN≥700 Giga/L) and baseline < 700 Giga/L or <uln (if="" giga="" l)<="" td="" uln≥700="">Two independent criteria	</uln>	Two independent criteria

Parameter	PCSV	Comments	
Urinalysis			
pН	 ≤4.6 or ≤LLN (if LLN≤4.6) and baseline > 4.6 or >LLN (if LLN≤4.6) ≥8 or ≥ULN (if ULN≥8) and baseline < 8 or <uln (if="" li="" uln≥8)<=""> </uln>	Two independent criteria	
Vital signs			
HR	<45 bpm and decrease from baseline ≥20 bpm ≥120 bpm and increase from baseline≥20 bpm	To be applied for all positions except STANDING	
SBP	≤95 mmHg and decrease from baseline ≥20mmHg ≥160 mmHg and increase from baseline ≥20 mmHg	To be applied for all positions except STANDING	
DBP	≤45 mmHg and decrease from baseline ≥10 mmHg ≥110 mmHg and increase from baseline ≥10 mmHg	To be applied for all positions except STANDING	
Weight	≥ 5% increase from baseline ≥5% decrease from baseline	FDA Feb 2007	

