5.8.2. Clinical Laboratory Measurements

Laboratory measurements include clinical chemistry and hematology results, and will be converted to standard international units and US conventional units. Summaries of laboratory variables based on standard international units will include:

- Descriptive statistics of laboratory result and change from baseline to Day 29. Summary statistics will include the number of patients, mean, median, standard deviation, quartiles, minimum, and maximum.
- Number and percentage of patients with a potentially clinically significant value (PCSV) at any post-randomization time point will be summarized for each clinical laboratory test for all patients and separately for patients in whom the PCSV criterion was normal or missing at baseline.
- Shift tables based on baseline normal/abnormal and other tabular and graphical methods may be used to present the results for parameters of interest.

Listing of all laboratory parameters normal range and abnormal flag by patient and visit will be provided.

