- 15. In **cohort 2 (and patients <18 years in cohort 3)**, each patient will be assigned at randomization by IWRS to a blood sample collection schedule for drug concentration and immunogenicity analysis. Actual dosing time and PK-ADA sample collection times will be recorded. To conserve blood volume, a single blood draw for drug concentration and immunogenicity will be obtained.
- 16. Patients will be followed by phone at day 120 and day 169 for vital status, pregnancy status, targeted safety information, and additional safety information in newborns of study participants. Refer to Section 9.2.5 for more information on these follow-up assessments.
- 17. For patients <12 years in cohort 2 and cohort 3, follow-up by phone will be conducted within 6 to 8 hours of infusion to collect the information indicated.

Parameter	PCSV	Comments
Clinical Chemis	try	
ALT*	>3 and \leq 5 ULN and baseline \leq 3 ULN*	Enzymes activities must be expressed in ULN, not in IU/L.
	>5 and ≤ 10 ULN and baseline ≤ 5 ULN	Concept paper on DILI – FDA draft Guidance Oct 2007.
	>10 and ≤ 20 ULN and baseline ≤ 10 ULN	Each category is calculated independently.
	>20 ULN and baseline ≤ 20 ULN	* At least one level is required; multiple levels are optional for phase 2/3 studies. If it is desirable to get the distribution across the different PCSV levels, additional shift table on $\leq 3, >3$ to $\leq 5, > 5$ to $\leq 10, >10$ to ≤ 20 , and > 20 category for baseline vs. post baseline may be provided
AST*	 >3 and ≤ 5 ULN and baseline ≤ 3 ULN* >5 and ≤ 10 ULN and baseline ≤ 5 ULN >10 and ≤ 20 ULN and baseline ≤ 10 ULN 	Enzymes activities must be expressed in ULN, not in IU/L. Concept paper on DILI – FDA draft Guidance Oct 2007. Each category is calculated independently.
	>20 ULN and baseline ≤ 20 ULN	* At least one level is required, multiple levels are optional for phase 2/3 studies. If it is desirable to get the distribution across the different PCSV levels, additional shift table on $\leq 3, >3$ to $\leq 5, > 5$ to $\leq 10, >10$ to ≤ 20 , and > 20 category for baseline vs. post baseline may be provided
Alkaline Phosphatase	>1.5 ULN and baseline \leq 1.5 ULN	Enzyme activity must be expressed in ULN, not in IU/L. Concept paper on DILI – FDA draft Guidance Oct 2007.

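### For ALT, AST, total bilirubin and CPK, the SAP's minimum PCSV table can leave out patients above the cap of the lowest band, and the bilirubin and CPK rows contradict their own counting comment

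*SAP*

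**What the plan says.** SAP Section 5.8.2 plans, for laboratory data, the number and percentage of patients with a PCSV at any time after randomization. These counts "will be summarized for each clinical laboratory test for all patients" and separately for patients who were normal or missing on the criterion at baseline. The section does not say which level applies where a test has several.

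The levels are in the criteria table of SAP Section 10.2:

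- **ALT and AST:** four bands, from above 3 and up to 5 ULN to ">20 ULN and baseline ≤ 20 ULN". The comment states: "Each category is calculated independently".
- **Total bilirubin:** above 1.5 and up to 2 ULN (baseline at or below 1.5 ULN), and above 2 ULN. The comment states: "Categories are cumulative".
- **CPK:** ">3 and ≤ 10 ULN and baseline ≤ 3 ULN", and above 10 ULN. The comment is the same as for bilirubin.

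The note on which levels to report reads "At least one level is required; multiple levels are optional for phase 2/3 studies" in the ALT row and "At least one level is required, multiple levels are optional for phase 2/3 studies" in the other three rows. The further shift tables are also optional. In all four rows the asterisk appears on the parameter name and on the lowest band, and on no other level.

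**The concern.** A first-level safety count is normally read as the number of patients who passed a threshold. With an upper cap, it becomes the number who had a value inside a mild band. If that band is the only one tabulated, a patient at 4 ULN adds to the count and a patient at 25 ULN may not, so an arm with the more severe elevations need not show the higher count.

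The PCSV count matters more than usual here because adverse event collection is targeted. Under Protocol Section 10.1.1, grade 3 and 4 events in phase 3 are collected as such only in cohort 2 and in cohort 3 patients under 18. In cohort 1, a severe but non-serious laboratory elevation that led to no medically-attended visit may not be recorded as an adverse event.

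For bilirubin and CPK the problem is different: the criterion and its comment cannot both be followed.

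**Working it through.** The plan states no figure to reproduce. The check applies the printed criteria as logical rules to simple profiles.

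**Rules**

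- Capped band (L, U], as printed: count the patient if baseline ≤ L and at least one post-baseline value x satisfies L < x ≤ U.
- Uncapped lowest level: count the patient if baseline ≤ L and the highest post-baseline value exceeds L.

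**Inputs**

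- From SAP Section 10.2, in ULN: (L, U) = (3, 5) for ALT and AST, (1.5, 2) for total bilirubin, (3, 10) for CPK.
- From the schedules of events: cohort 1 has post-baseline chemistry on days 7, 15 and 29, so three values are used. Pediatric patients under 10 kg have two (days 7 and 29).
- Assumed for illustration: baseline 1 ULN and the profiles below.

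| Test | Post-baseline values (ULN) | Capped lowest band | Uncapped lowest level |
|---|---|---|---|
| ALT/AST | 4, 1, 1 | counted | counted |
| ALT/AST | 7, 1, 1 | not counted | counted |
| ALT/AST | 15, 1, 1 | not counted | counted |
| ALT/AST | 25, 1, 1 | not counted | counted |
| ALT/AST | 25, 4, 1 | counted | counted |
| Bilirubin | 1.8, 1, 1 | counted | counted |
| Bilirubin | 3, 1, 1 | not counted | counted |
| Bilirubin | 6, 1, 1 | not counted | counted |
| Bilirubin | 6, 1.8, 1 | counted | counted |
| CPK | 5, 1, 1 | counted | counted |
| CPK | 12, 1, 1 | not counted | counted |
| CPK | 40, 1, 1 | not counted | counted |
| CPK | 40, 5, 1 | counted | counted |

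**Reading the table**

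1. ALT and AST: the comment makes the bands separate, so the capped column is what the lowest band alone would show. The 7, 15 and 25 ULN profiles drop out unless a second sample lands between 3 and 5 ULN, as in the fifth row.
2. Bilirubin and CPK: the capped column follows the printed criterion and the uncapped column follows the comment. They disagree on two of four profiles for each test. The SAP does not say which governs.
3. Neighbouring rows of the same table have no cap: alkaline phosphatase above 1.5 ULN, lipase and amylase at or above 3 ULN, CRP above 2 ULN. An uncapped first level would match them.

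**What cannot be computed.** The share of patients lost depends on the distribution of peak values and on how often a second sample falls inside the band. The documents give neither, so no percentage is offered.

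**The case against.** The strongest reply is that the SAP never tells anyone to report the lowest band alone. The note asks for at least one level and names none, and the asterisk also sits on the parameter names, so it may only point to the note. All four ALT and AST bands are listed as criteria. If all are tabulated, a patient starting from 3 ULN or below who later exceeds 5 ULN is counted in a higher band. This stands: a reader might infer that the mildest band is the only required level, and the text does not say so. The hematology rows use an asterisk for default criteria, which supports the inference without settling it. What remains is that the minimum can be met by a table that omits the higher values, and that the level to be reported is not fixed in advance.

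Second, for bilirubin and CPK the cumulative comment would bring every severe value into the first level. This also stands. A reader might infer that severe bilirubin and CPK cases are lost, but that follows only if the printed cap overrides the comment. The supportable finding in these two rows is the contradiction.

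Third, high values are visible elsewhere. SAP Section 5.8.2 provides a by-patient listing with abnormal flags and descriptive statistics that include the maximum. A separate uncapped row covers ALT above 3 ULN with bilirubin above 2 ULN. Protocol Section 9.2.7 requires the investigator to review all laboratory values and to repeat significantly abnormal ones. This is correct, and no monitoring action depends on PCSVs. But a listing gives no count by arm, a maximum shows one patient, and the combined row needs both abnormalities, so an isolated ALT of 25 ULN does not qualify.

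**Conclusion.** The point holds in a limited form. For ALT and AST, a table confined to the asterisked band satisfies the SAP's minimum and omits a patient who goes from 3 ULN or below to above 5 ULN, unless another sample falls between 3 and 5 ULN. This assumes that only that band is tabulated, which the SAP permits but does not direct. For total bilirubin and CPK, the capped criteria and the cumulative comment conflict, and the two readings give different counts from the same data.

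The documents do not support saying that severe elevations would be hidden from the safety data, or that a given share of patients would be lost. Any such share would rest on assumed peak distributions. The effect is confined to the PCSV counts by arm; the primary efficacy analysis and the laboratory listings are not affected. It is worth correcting because it changes a safety comparison between arms and the correction is small.

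**What to change.** In SAP Section 10.2:

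1. Remove the upper cap from the lowest level in the four rows, keeping the existing baseline conditions: ALT above 3 ULN, AST above 3 ULN, total bilirubin above 1.5 ULN, CPK above 3 ULN.
2. State that this level is always tabulated, and replace the note that makes further levels optional.
3. Tabulate the higher levels already listed as well. They are needed because the baseline conditions differ by level: a patient with baseline ALT of 4 ULN and a peak of 12 ULN fails the baseline condition of the lowest level and can be counted only at a higher one.
4. Use one counting rule across the four rows, worded so that the printed criteria and the comments agree.

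The cost is revised wording in four table rows and a few more lines in the PCSV tables. No new data are needed.

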10.3. Symptom Evolution of COVID-19 (SE-C19)

Symptom Evolution of COVID-19 (SE-C19): The SE-C19 was developed based on the symptoms listed by the CDC, published literature and supported by interviews with patients with COVID-19. The symptom diary included a list of 23 symptoms (feverish, chills, sore throat, cough, shortness of breath or difficulty breathing, nausea, vomiting, diarrhea, headache, red or watery eyes, body aches, loss of taste or smell, fatigue, loss of appetite, confusion, dizziness, pressure or tight chest, chest pain, stomachache, rash, sneezing, sputum/phlegm, runny nose). On a daily basis, patients indicated which of the 23 symptoms they had experienced in the last 24 hours, and then rated each symptom selected at its worst moment in the last 24 hours on a scale of mild, moderate or severe. Each symptom), or 3 (severe symptom). For the purposes of analysis, 'no symptom' will be assigned a score of 0, 'mild symptom' and 'moderate symptom' will be assigned a score of 2 (ie, the mild and moderate symptom categories will be collapsed).

Signature Page for VV-RIM-00147241 v1.0

ESig Approval	PPD PPD
	PPD
	12-Mar-2021 18:48:27 GMT+0000

ESig Approval	PPD PPD
	PPD
	12-Mar-2021 18:50:05 GMT+0000

ESig Approval	PPD PPD
	PPD
	12-Mar-2021 19:01:59 GMT+0000

ESig Approval	PPD PPD
	12-Mar-2021 22:22:47 GMT+0000

ESig Approval	PPD PPD PPD
	12-Mar-2021 22:28:34 GMT+0000

ESig Approval	PPD			
	PPD			
	PPD			
	12-Mar-2	2021 22	2:30:07 GMT+0	000

Signature Page for VV-RIM-00147241 v1.0 Approved

Signature Page for VV-RIM-00147241 v1.0

ESig Approval	PPD
	PPD
	PPD
	12-Mar-2021 23:34:26 GMT+0000

Signature Page for VV-RIM-00147241 v1.0 Approved
